#### 4.2. Inclusion Criteria

Subjects must meet all of the following inclusion criteria to be eligible for participation in this study. Additional indication-specific inclusion criteria for 1000 mg BID Dose Escalation Cohort and Phase 2 are provided in [Appendix 3](#).

- 1) Male or female  $\geq 18$  years of age
- 2) Dose Escalation Cohorts: Histologically or cytologically confirmed advanced malignant solid tumor that is refractory to or intolerant of all standard therapy or for which no standard therapy is available.
- 3) Dose Expansion and 1000 mg BID Dose Escalation Cohorts: Subjects must have available sufficient and adequate formalin-fixed tumor sample preferably from a biopsy of a tumor lesion obtained either at the time of or after the diagnosis of advanced disease has been made and from a site not previously irradiated. Alternatively, subjects must agree to have a biopsy taken prior to entering the study to provide adequate tissue. For the 1000 mg BID dose escalation cohort, subjects with melanoma, Merkel cell, MSI-H cancers, and cHL are not required to have archival or fresh biopsy tissue.

CCI

- 5) All persisting toxic effects of any prior antitumor therapy resolved to National Cancer Institute-Common Terminology Criteria for Adverse Events (NCI-CTCAE) version 5.0 Grade  $\leq 1$  or baseline before the first dose of study drug (with the exception of alopecia [Grade 1 or 2 permitted] and neurotoxicity [Grade 1 or 2 permitted]).
- 6) Eastern Cooperative Oncology Group (ECOG) Performance Status of  $\leq 2$
- 7) Life expectancy of  $\geq 3$  months, in the opinion of the investigator
- 8) Adequate organ function defined as follows:
  - a) Hematologic: Platelets  $\geq 100 \times 10^9/L$  ( $\geq 60 \times 10^9/L$  in subjects with HCC); Hemoglobin  $\geq 9.0$  g/dL; ANC  $\geq 1.5 \times 10^9/L$  (without blood transfusion, platelet transfusion, or growth factors within previous 7 days of the hematologic laboratory values obtained at screening visit)
  - b) Hepatic: AST/ALT  $\leq 2.5 \times$  upper limit of normal (ULN) (if liver metastases are present,  $\leq 5 \times$  ULN); total or conjugated bilirubin  $\leq 1.5 \times$  ULN
  - c) Renal: Creatinine clearance ( $CL_{cr}$ )  $\geq 45$  mL/min as calculated by the Cockcroft-Gault method

- 9) Coagulation: Subjects on full-dose oral anticoagulation, except warfarin, which is an excluded medication, must be on a stable dose (minimum duration 14 days). Subjects on low molecular weight heparin will be allowed.
- 10) Negative serum pregnancy test for female subjects
- 11) Male subjects and female subjects of childbearing potential who engage in heterosexual intercourse must agree to use protocol-specified method(s) of contraception as described in [Appendix 5](#).
- 12) Females who are nursing must agree to discontinue nursing before the first dose of GS-4224.
- 13) Able and willing to provide written informed consent to participate in the study
- 14) Patients with history of human immunodeficiency virus (HIV) infection should have a CD4+ T-cell count  $\geq 350$  cells/ $\mu$ L at screening.
- 15) Patients with serological evidence of chronic HBV should have HBV viral load below the limit of quantification at screening.
- 16) Patients with serological evidence of hepatitis C virus infection (HCV) should have completed curative antiviral treatment and have HCV viral load below the limit of quantification at screening.

#### 4.3. Exclusion Criteria

Subjects who meet *any* of the following exclusion criteria are not to be enrolled in this study. Additional indication-specific exclusion criteria for 1000 mg BID Dose Escalation Cohort and Phase 2 are provided in [Appendix 3](#).

- 1) History or evidence of clinically significant disorder, condition, or disease that, in the opinion of the investigator or medical monitor would pose a risk to subject safety or interfere with the study evaluations, procedures, or completion.
- 2) Dose Escalation Cohorts: History of  $\geq$  Grade 3 AEs during prior treatment with an immune checkpoint inhibitor, or history of discontinuation of treatment with an immune checkpoint inhibitor due to AEs.
- 3) Dose Escalation 1000 mg BID and Dose Expansion Cohorts: Prior treatment with an immune checkpoint inhibitor (anti-PD-1, anti-PD-L1, or anti-PD-L2 antibodies).
- 4) History of autoimmune disease (for example, systemic lupus erythematosus, rheumatoid arthritis, inflammatory bowel disease, vascular thrombosis associated with antiphospholipid syndrome, Wegener's granulomatosis, Sjögren's syndrome, Bell's palsy, Guillain-Barré syndrome, multiple sclerosis, autoimmune thyroid disease, vasculitis, or glomerulonephritis).
- 5) Positive serum pregnancy test ([Appendix 5](#))

- 6) Patient has known active central nervous system (CNS) metastases and/or carcinomatous meningitis. Patients with previously treated brain metastases may participate provided they are clinically stable for at least 4 weeks prior to study entry, have no evidence of new or enlarging brain metastases and if taking corticosteroids, are on stable or decreasing doses for at least 7 days from first dose of study drug.
- 7) Uncontrolled intercurrent illness including, but not limited to, active uncontrolled infection, active or chronic bleeding event within 28 days prior to first dose of study drug, or psychiatric illness/social situation that would limit compliance with study requirements as judged by treating physician.
- 8) Myocardial infarction, symptomatic congestive heart failure (New York Heart Association Classification > Class II), unstable angina, or serious uncontrolled cardiac arrhythmia within the last 6 months of first dose of study drug.
- 9) Major surgery, defined as any surgical procedure that involves general anesthesia and a significant incision (ie, larger than what is required for placement of central venous access, percutaneous feeding tube, or biopsy) within 28 days of the first dose of study drug.
- 10) Impairment of GI function or GI disease that may significantly alter the absorption of GS-4224, including any unresolved nausea, vomiting, or diarrhea that is Common Terminology Criteria for Adverse Events (CTCAE) Grade > 1.
- 11) Symptomatic ascites or pleural effusion. A patient who is clinically stable following treatment for these conditions (including thora- or para-centesis) is eligible.
- 12) Minor surgical procedure(s) within 7 days of enrollment, or not yet recovered from prior surgery (placement of central venous access device, fine needle aspiration, or endoscopic biliary stent  $\geq$  1 day before enrollment is acceptable).
- 13) Prior systemic radiation therapy completed within 4 weeks of the first dose of study drug, prior local radiation therapy completed within 2 weeks of Cycle 1 Day 1 (C1D1), or radiopharmaceuticals (strontium, samarium) within 8 weeks of C1D1.
- 14) Antitumor therapy (chemotherapy, antibody therapy, molecular targeted therapy) within 21 days or 5 half-lives, whichever is longer, of study drug dosing (6 weeks for nitrosoureas, mitomycin C, or molecular agents with  $t_{1/2} > 10$  days); concurrent use of hormone therapy for prostate cancer is permitted.
- 15) History of long QT syndrome or additional risk factors for Torsades de Pointes or whose corrected QT interval (QTc) measured (Fridericia method) at screening is prolonged ( $> 480$  ms).
- 16) Use of concomitant medications that prolong QT/QTc interval at screening
- 17) Clinically significant bleeding within 28 days of the first dose of study drug

- 18) Known hypersensitivity to study drug, the metabolites, or formulation excipients
- 19) Use of any prohibited concomitant medications as described in Section 5.5 and any investigational agent within 2 weeks of study treatment initiation
- 20) Breastfeeding female
- 21) Received live virus vaccination within 30 days of first dose of study treatment. Seasonal flu vaccines that do not contain live virus are permitted.
- 22) History of hematologic stem cell transplant or solid organ transplant

## **5. INVESTIGATIONAL MEDICINAL PRODUCTS**

### **5.1. Randomization, Blinding and Treatment Codes**

An IXRS will be employed to manage the conduct of the study. In Phase 1b and/or Phase 2, the IXRS will be used to maintain a central log documenting enrollment, to manage dose modifications, to assess current inventories of study drug, to initiate any necessary resupply of study drug, and to document discontinuation of study drug and study participation.

This is an open-label study in both the dose escalation (Phase 1b) and the dose expansion (Phase 2) portions of the study.

### **5.2. Description and Handling of GS-4224**

#### **5.2.1. Formulation**

GS-4224 tablets are prepared using GS-4224-03 (bis-fumarate salt). Orange, film-coated tablets are available at a strength of 100 mg (free base equivalent) and are supplied as orange, capsule-shaped, plain-faced, film-coated tablets. In addition to the active ingredient, each orange, film-coated tablet contains the following inactive ingredients: mannitol, microcrystalline cellulose, crospovidone, magnesium stearate, polyvinyl alcohol, titanium dioxide, polyethylene glycol, talc, iron oxide yellow, iron oxide red, and ferrousferrous oxide.

Green, film-coated tablets are also prepared using GS-4224-03 (bis-fumarate salt) and are available in strengths of 100 mg, 200 mg, and 500 mg (free base equivalent). The 100-mg-strength tablets are supplied as green, round, film-coated tablets that are debossed with “GSI” on one side of the tablet and “100” on the other side of the tablet. The 200-mg-strength tablets are supplied as green, round, film-coated tablets that are debossed with “GSI” on one side of the tablet and “200” on the other side of the tablet. The 500-mg-strength tablets are supplied as green, capsule-shaped, film-coated tablets that are debossed with “GSI” on one side of the tablet and “500” on the other side of the tablet. In addition to the active ingredient, each green, film-coated tablet contains the following inactive ingredients: microcrystalline cellulose, crospovidone, magnesium stearate, polyvinyl alcohol, titanium dioxide, polyethylene glycol, talc, iron oxide yellow, and ferrousferrous oxide.

#### **5.2.2. Packaging and Labeling**

GS-4224 tablets are packaged in white, high density polyethylene bottles. Each bottle contains 30 tablets, silica gel desiccant, and polyester packing material. Each bottle is capped with a child-resistant polypropylene screw cap fitted with an induction sealed, aluminum-faced liner.

Study drug(s) to be distributed to centers in participating countries shall be labeled to meet applicable requirements of the FDA, European Union (EU) Guideline to Good Manufacturing Practice - Annex 13 (IMP), and/or other local regulations.

### **5.2.3. Storage and Handling**

GS-4224 tablets should be stored refrigerated (2-8°C). Storage conditions are specified on the label. Keep bottles tightly closed to protect from moisture and allow them to warm to room temperature prior to opening. When a 100-mg bottle is removed from storage for dosing, keep tightly closed when not in use and store below 30°C for up to 4 weeks (28 days). The 200-mg and 500-mg tablets may be stored below 30°C for up to 12 weeks (84 days). Until dispensed to the subjects, all study drug bottles should be stored in a securely locked area, accessible only to authorized site personnel. To ensure the stability and proper identification, the drug products should be stored in the containers in which they were supplied.

### **5.3. Dosage and Administration of GS-4224**

The GS-4224 study drug will be supplied as tablets in strengths of 100 mg, 200 mg, and/or 500 mg. GS-4224 will be taken once daily in the morning (400 1500 mg QD cohorts) and 1000 mg twice daily separated by approximately 12 hours (1000 mg BID cohort).

On days with intensive PK (Cycle 1 Days 1 and 15), study drug will be administered at the same time every morning with approximately 240 mL of water and following an overnight fast (no food or drinks, except water, for at least 8 hours). For study treatments including those of more than 5 tablets, up to an additional 120 mL of water can be administered, if necessary. Water will be withheld starting 1 hour before and for 2 hours after dose administration, except for water given with the study drug. Water may be consumed by subjects following the 2-hour blood draw for the remainder of the collection period. A meal (standardized lunch) will be provided to subjects after the 4 hour postdose blood draw. All other fluids will be allowed after the 4 hour postdose blood draw.

For all days that study drug is administered where no intensive PK assessments are required, GS-4224 should be administered without regard to food at approximately the same time every morning. Subjects should administer study drug with a full glass of water.

If vomiting occurs after administration of study drug, the dose should not be repeated.

### **5.4. Dose Modifications and Treatment Interruption of GS-4224**

#### **5.4.1. Dose Modifications**

For Dose Escalation 400 1500 mg QD cohorts, after completing 4 cycles of treatment and C5D1 scans, subjects receiving GS-4224 at a dose level below that which has been deemed to be safe by the SRT may, at the investigator's discretion, receive GS-4224 at the highest dose deemed to be safe by the SRT. **CCI**

#### 5.4.2. Treatment Interruption for GS-4224

The following qualifying AEs must lead to interruption of GS-4224 administration, unless there is another obvious attribution (eg, trauma, PD):

- Dose interruption should occur for Grade  $\geq 3$  serum creatinine (more than  $3\times$  baseline) toxicity;
- Dose interruption should occur in subjects with any Grade 3 or Grade 4 elevation in AST or ALT associated with a Grade 2 elevation in bilirubin;
- Any Grade  $\geq 3$  non-skin, drug-related AE with the following exceptions:

Do not interrupt treatment for Grade  $\geq 3$  fatigue

- Any Grade  $\geq 3$  drug-related laboratory abnormality with the following exceptions for lymphopenia:

Grade 3 lymphopenia does not require a dose interruption

- Any AE, laboratory abnormality, or intercurrent illness which, in the judgment of the investigator, warrants interrupting the dose of study drug

Subjects receiving GS-4224 who have drug-related toxicities that meet the criteria for dose interruption should have GS-4224 interrupted until criteria to resume treatment are met.

**Note:** GS-4224 should be discontinued in subjects who experience any Grade  $\geq 3$  skin drug-related AE with systemic signs or symptoms or suspected Stevens-Johnson syndrome (SJS) or toxic epidermal necrolysis (TEN).

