#### 5.4.3. Management of Immune-Related Adverse Events

Immuno-oncology agents such as GS-4224 are associated with irAEs. Early recognition and management of irAEs may mitigate severe toxicity. Investigators should also monitor subjects closely for potential irAEs, which may manifest after weeks of treatment, at the earliest. Such events may consist of persistent rash, diarrhea, colitis, autoimmune hepatitis, pneumonitis, encephalitis, arthritis, glomerulonephritis, cardiomyopathy, or uveitis and other inflammatory eye conditions.

Management algorithms have been developed to assist investigators in assessing and managing the following groups of irAEs: GI, pulmonary, dermatological, renal, hepatic, neurological, and endocrine, among others.

AEs (both non-serious and serious) associated with drug exposure and consistent with an immune phenomenon may represent an immunologic etiology. These irAEs may be predicted based on the nature of the study drugs, their mechanism of action, and reported experience with immunotherapies that have a similar mechanism of action. An irAE can occur any time from shortly after the first dose to several months after the last dose of treatment. Particular attention should be paid to AEs that may be suggestive of potential irAEs, as outlined below.

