**Table 5-2. Gastrointestinal (GI) irAE Management Algorithm**

Gastrointestinal (GI) irAEs		
CTCAE Grade of Diarrhea/Colitis	Management	Follow Up

Grade 1                      Diarrhea: < 4 stools/day over baseline.                      Colitis: asymptomatic.
	
Continue GS-4224 therapy per protocol.                      Symptomatic treatment.
	
Close monitoring for worsening symptoms.                      Educate subject to report worsening immediately.                      Consider symptomatic treatment including hydration, electrolyte replacement, dietary changes (eg, American Dietetic Association colitis diet), and loperamide.  If worsens: Treat as Grade 2 or 3-4.

Grade 2                      Diarrhea: 4-6 stools per day over baseline; IV fluids indicated < 24 h; not interfering with activities of daily living (ADL).                      Colitis: abdominal pain; blood in stool.
	
Interrupt GS-4224 therapy per protocol.                      Symptomatic treatment.
	
If improves to Grade 1: Resume GS-4224 therapy per protocol.  If persists > 5 to 7 days or recurs: 0.5-1 mg/kg/day methylprednisolone or equivalent.                      When symptoms improve to Grade 1, taper corticosteroids over <math>\geq 1</math> month; consider prophylactic antibiotics for opportunistic infections; resume GS-4224 therapy per protocol.  If worsens or persists > 3 to 5 days with oral corticosteroids: Treat as Grade 3-4.

Grade 3-4                      Diarrhea (Grade 3): <math>\geq 7</math> stools per day over baseline; incontinence; IV fluids <math>\geq 24</math> h; interfering with ADL.                      Colitis (Grade 3): severe abdominal pain, medical intervention indicated, peritoneal signs.                      Grade 4: life-threatening, perforation
	
Discontinue GS-4224 therapy per protocol.                      1-2 mg/kg/day methylprednisolone IV or equivalent.                      Add prophylactic antibiotics for opportunistic infections.                      Consider lower endoscopy.
	
If improves: Continue corticosteroids until Grade 1, then taper over <math>\geq 1</math> month.  If persists > 3 to 5 days or recurs after improvement: Add infliximab 5 mg/kg (if no contraindication).  Note: Infliximab should not be used in cases of perforation or sepsis.

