**Table 5-4. Hepatic irAE Management Algorithm**

Hepatic irAEs		
CTCAE Grade of Liver Test Elevation	Management	Follow Up
Grade 1 AST or ALT > ULN to 3 × ULN or total bilirubin > ULN to 1.5 × ULN	Continue GS-4224 therapy per protocol	Continue liver function tests (LFT) monitoring per protocol. If worsens: Treat as Grade 2 or Grade 3-4.
Grade 2 AST or ALT > 3 to ≤ 5 × ULN or total bilirubin > 1.5 to ≤ 3 × ULN	Interrupt GS-4224 therapy per protocol Increase frequency of monitoring to every 3 days If subject has concurrent AST or ALT > 3 × ULN and total bilirubin > 2 × ULN, discontinue GS-4224 therapy per protocol.	If returns to baseline: Resume routine monitoring; resume GS-4224 therapy per protocol. If elevations persist > 5 to 7 days or worsen: 0.5-1 mg/kg/day methylprednisolone IV or oral equivalent. When LFT returns to Grade 1 or baseline, taper corticosteroids over ≥ 1 month, consider prophylactic antibiotics for opportunistic infections, and resume GS-4224 therapy per protocol.
Grade 3-4 AST or ALT > 5 × ULN and/or total bilirubin > 3 × ULN.	Discontinue GS-4224 therapy per protocol Increase frequency of monitoring to every 1-2 days 1-2 mg/kg/day methylprednisolone IV or oral equivalent.* Add prophylactic antibiotics for opportunistic infections Consult gastroenterology Consider obtaining MRI/CT scan of liver and liver biopsy if clinically warranted	If returns to Grade 2: Taper corticosteroids over ≥ 1 month. If does not improve in > 3 to 5 days, worsens or rebounds: Add mycophenolate mofetil 1 g twice daily. If no response within an additional 3-5 days, consider other immunosuppressants per local guidelines.

\* The recommended starting dose for Grade 4 hepatitis is 2 mg/kg/day methylprednisolone IV.  
 ALT alanine aminotransferase; AST aspartate aminotransferase; CT computed tomography; CTCAE Common Terminology Criteria for Adverse Events; irAE immune related adverse event; IV intravenous(ly); LFT liver function test; MRI magnetic resonance imaging; ULN upper limit of normal

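### Section 5.4.2 holds GS-4224 for severe toxicity without saying when it may restart, and differs from the irAE tables on rechallenge, most clearly after combined liver injury

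*Protocol*

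**What the plan says.** **Section 5.4.2.** The listed events "must lead to interruption of GS-4224 administration, unless there is another obvious attribution". There are five triggers: serum creatinine of Grade 3 or above; "any Grade 3 or Grade 4 elevation in AST or ALT associated with a Grade 2 elevation in bilirubin"; any drug-related non-skin AE of Grade 3 or above (except fatigue); any drug-related laboratory abnormality of Grade 3 or above (except Grade 3 lymphopenia); and investigator judgment. Affected subjects "should have GS-4224 interrupted until criteria to resume treatment are met". The only permanent stop in the section is for severe drug-related skin events with systemic signs and for suspected SJS or TEN.

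**Section 5.4.3 and Tables 5-1 to 5-7.** The tables are introduced this way: "Management algorithms have been developed to assist investigators in assessing and managing the following groups of irAEs". Section 5.5.2 refers to them as guidance. In Table 5-4 the Grade 3-4 row is defined as "AST or ALT > 5 × ULN and/or total bilirubin > 3 × ULN" and its action is "Discontinue GS-4224 therapy per protocol Increase frequency of monitoring to every 1-2 days". The Grade 2 row adds a stop when AST/ALT exceeds 3 × ULN together with "total bilirubin > 2 × ULN, discontinue GS-4224 therapy per protocol". Table 5-2 (Grade 3-4) likewise says "Discontinue GS-4224 therapy per protocol", as do Tables 5-3 and 5-7 at Grade 3-4 and Table 5-6 at Grade 4. In Table 5-6, Grade 2-3 creatinine elevation that lasts more than 7 days or worsens is treated as Grade 4.

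**Sections 1.5, 6.10.1 and 3.5.** Section 1.5 says the discontinuation parameters are in 6.10.1. One of the nine items in 6.10.1 refers permanent treatment-discontinuation criteria to Section 3.5. Section 3.5 lists reasons to stop the study or recruitment at a center.

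**The concern.** A hold rule needs an exit. Here the exit is mentioned but not defined, and a second set of rules gives a different end point for some of the same events. Two sites, each following the protocol, could reach opposite rechallenge decisions in subjects with the same liver results: one restarts under 5.4.2 after recovery, the other stops for good under Table 5-4. The place a reader would go to settle it, 6.10.1, leads to a section with no subject-level criteria. What is at stake is the safety of re-exposure after severe toxicity, and consistent handling across sites.

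**Working it through.** The plan states no figure on this point, so the check sets the texts side by side.

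**1. Does 5.4.2 contain a restart rule?** It has 5 triggers and 0 resume criteria, and it cites no other section for them. A redaction closes Section 5.4.1, after the rule on intra-subject dose increases; 5.4.2 itself shows none.

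**2. Do the tables supply one?** In part.
- Rows with a written resume step: Table 5-1 (2), the Grade 2 rows of 5-2, 5-3, 5-4 and 5-7 (4), symptomatic endocrinopathy in 5-5 (1), Grade 2-3 in 5-6 (1). Total 2 + 4 + 1 + 1 = 8.
- Rows that discontinue with no resume step: Grade 3-4 in 5-2, 5-3, 5-4 and 5-7 (4) and Grade 4 in 5-6 (1). Total 4 + 1 = 5.
- The adrenal-crisis row of Table 5-5 allows either action and is in neither count.

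For events of Grade 3 or above, a restart step exists only for dermatological irAEs, Grade 3 renal irAEs and symptomatic endocrinopathy (not graded). Drug-related events that are not immune-related have none.

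**3. The liver case.** This uses Table 5-4's cut-offs as the grade boundaries: Grade 3-4 AST/ALT is > 5 × ULN, and Grade 2 bilirubin is > 1.5 to ≤ 3 × ULN.

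| AST/ALT (× ULN) | Bilirubin (× ULN) | Section 5.4.2 | Table 5-4, if immune-related |
|---|---|---|---|
| > 5 | > 1.5 to ≤ 3 | Interrupt (hepatic bullet) | Discontinue (Grade 3-4 row) |
| > 5 | ≤ 1.5 | Interrupt if drug-related (laboratory bullet) | Discontinue (Grade 3-4 row) |
| > 5 | > 3 | Interrupt if drug-related (laboratory bullet; the hepatic bullet names Grade 2 bilirubin only) | Discontinue (Grade 3-4 row) |
| > 3 to ≤ 5 | > 2 to ≤ 3 | No named trigger; investigator judgment | Discontinue (Grade 2 row) |

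Every combination covered by the hepatic bullet has AST/ALT > 5 × ULN. It therefore lies wholly inside Table 5-4's Grade 3-4 row whenever the event is judged immune-related.

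**4. Other organs.** GI, pulmonary and neurological irAEs of Grade 3-4 are interrupted under 5.4.2 if drug-related and discontinued under their tables. For renal irAEs the two agree on Grade 3 creatinine at first (interrupt). They part at Grade 4, and also when a Grade 2-3 elevation persists beyond 7 days or worsens.

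**5. Is there a tie-breaker?** No sentence ranks 5.4.2 against the tables. The path from 1.5 to 6.10.1 to 3.5 ends at four study-level reasons, a health-authority stop and a center-recruitment stop, with 0 subject-level criteria. The other items in 6.10.1 that could apply are an event matching an exclusion criterion, unacceptable toxicity and intercurrent illness. All three rest on investigator or sponsor judgment.

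**The case against.** The strongest reply is that the two rules work in sequence. Section 5.4.2 is a general hold for drug-related toxicity. The tables apply once non-inflammatory causes are ruled out, and where a table discontinues, the criteria to resume are simply never met. That is a sensible reading and may be what was intended. It is not written down, however, and it leaves drug-related events that are not immune-related, including combined liver injury, with no restart threshold.

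Other safeguards exist. Section 6.2.9 requires laboratory results to be reviewed and acceptable before dosing, although it sets no grade. Section 6.10.1 lets the investigator, and for some items the sponsor, stop treatment. The SRT Charter (Section 3.2.3) is to hold individual stopping rules; it is not among the documents, and neither 5.4.2 nor 6.10.1 cites it. Sending actions back to the protocol also works in one case: Table 5-1's choice between interrupting and discontinuing maps onto the skin note in 5.4.2. These points narrow the problem without closing it.

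Three stronger readings are tempting and are not supported.
- A reader might infer that the protocol gives no restart thresholds at all. Eight table rows do.
- A reader might infer that sites are free to rechallenge after Grade 3 myocarditis or encephalitis, because myocarditis has no table and Table 5-7 allows Grade 2 neurological events to resume. Section 3.2.1.1 names both as irAEs calling for permanent discontinuation, and 5.5.2 directs sites to ASCO or institutional guidance. Rechallenge would require reading 5.4.2 in isolation.
- A reader might infer that the DLT definition must be changed to say that a discontinue row counts as a DLT. A toxicity for which drug is stopped for good already fits the item on events that preclude further dosing. DLT incidence is the primary endpoint, and rewording it now would redefine that endpoint after escalation data exist.

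**Conclusion.** The concern holds as a gap and an inconsistency in the rechallenge rules. Section 5.4.2 promises resume criteria that it does not give. It conflicts with Table 5-4 over combined liver injury, and with four other tables for severe irAEs, with no statement of precedence. The reference in 6.10.1 leads to the wrong kind of section. Both routes stop drug immediately, so no subject is left on drug during the acute event by this conflict.

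The documents give no event rate, so the size can be stated only as text counts: 5 triggers with 0 resume criteria, and 5 table rows that discontinue without a resume step. These counts do not measure how many subjects are affected. The SAP Introduction reports that the study ended early in Phase 1b, that Phase 2 was not started, and that subjects on study continue to be treated and/or followed. The practical effect is therefore limited to subjects still being dosed. The conclusion assumes Table 5-4's cut-offs as the grade boundaries and that no unseen document supplies the missing rule.

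**What to change.** 1. **Section 5.4.2, hepatic bullet.** Make both of these permanent discontinuations: Grade 3-4 AST/ALT with bilirubin of Grade 2 or above, and AST/ALT > 3 × ULN with bilirubin > 2 × ULN. Keep the exception for a clear alternative cause. It matters because Section 4.2 admits subjects with liver metastases at AST/ALT up to 5 × ULN, so some may meet the 3 × ULN part at entry.
2. **Section 5.4.2, precedence and restart.** State that Tables 5-1 to 5-7 govern interruption, resumption and discontinuation for events judged immune-related, with two provisos. The skin/SJS/TEN note overrides Table 5-1, and encephalitis of any grade and myocarditis of Grade 3 or above are permanently discontinued, in line with 3.2.1.1. For other drug-related events, allow restart on recovery to Grade 1 or lower, or to baseline.
3. **Section 6.10.1.** Replace the reference to Section 3.5 with Sections 5.4.2 to 5.4.10.

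Leave the DLT definition as it is.

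The cost is amendment wording and its ethics-committee approval, with no added visits, tests or subjects. The downside is that a few subjects who might have tolerated re-exposure lose the option.
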